## 5. RANDOMIZATION AND BLINDING

The following are required for subject randomization to occur:

- Trigger from site via electronic data capture (EDC) that a subject is ready for randomization.
- Analysis of blood samples to determine cohort assignment (Primary or Exploratory) based on presence or absence of DSA to available donors.
- Identification of donor cell lines for which the subject is compatible.
- Strata membership: recent MI (“Recent”) or chronic MI (“Chronic”).

The Primary Randomized Cohort and the Exploratory Randomized Cohort will be randomized separately. Subjects will be randomized 2:1 CAP-1002:placebo within each stratum using random block sizes of 3 and 6 and institutional balancing in an interactive web-based system (IWRS). Notification that a subject has been randomized will be sent to an independent storage/distribution center (depot). The depot will have password protected access to the randomization assignment and will randomly assign subjects in the Primary Randomized Cohort to an appropriate donor (or placebo). Subjects in the Exploratory Randomized Cohort will be randomly assigned to one of the available donors regardless of compatibility (based upon available inventory).

Both investigators and subjects will be blinded to treatment assignment throughout the trial. Core and central laboratory personnel analyzing the MRI images and testing serum for serial donor specific antigen and whole blood for cellular immune response will also be blinded throughout the trial, as will the CEC adjudicating events, and all medical affairs and clinical operations staff, except as noted below. Personnel at the MRI core laboratory will be blinded to treatment assignment but not temporal order of the images; e.g., readers will have access to and will use baseline and Month 6 images when reading Month 12 images as part of the informed reading protocol. A member of the Sponsor staff will be unblinded if an emergency blind break is required at any time during the trial. Study sites will be trained regarding the emergency unblinding process. Should a medical event occur that necessitates unblinding, the process will be accessible to investigators 24 hours a day and will include an emergency Sponsor contact.

The distribution of IP will occur in validated dry vapor shippers allowing for consistent transportation and scheduling flexibility at all sites. Both CAP-1002 and placebo will be packaged in identical cryogenic bags with similar labels. At the clinical site, the IP is thawed to room temperature, prepared and drawn into masked (with amber/transparent tape) syringes. The amber/transparent tape will allow the treating physician to see air bubbles but obscure the clarity of the IP suspension. Specific instructions for use are provided to each investigative site for reference. Central laboratories will be used to assess sensitization to CAP-1002 [i.e., single antigen bead (SAB), enzyme-linked immunosorbent spot (ELISpot) assay]. Because these results may unblind, they will not be shared with investigators, subjects, site personnel, or Sponsor staff in order to preserve blinding.

The DSMB, including a statistician independent of the sponsor's clinical trial team, will have access to unblinded data and immunological test results. In addition, as a result of administrative interim efficacy analyses (see [Section 13.2.2](#)), a prespecified group of personnel from the Sponsor (the smallest group possible), as well as personnel from Janssen Biotech, Inc. ("Janssen") in order to comply with the terms of that certain Collaboration Agreement and License Option, will become unblinded and will have full access to the efficacy data.

A list will be maintained in the trial master file to track any persons unblinded during the trial.

## 6. ANALYSIS POPULATIONS

The following analysis populations are defined for the trial:

**Primary Safety Population:** All subjects in the Primary Randomization Cohort who received the IP. Subjects will be summarized and analyzed per treatment actually received, regardless of their randomization assignment.

**Primary Intent-to-Treat (ITT) Population:** All subjects in the Primary Randomization Cohort who were randomized. Subjects will be summarized and analyzed per their randomization assignment, regardless of the treatment actually received.

**Primary Modified Intent-to-Treat (mITT) Population:** For a given efficacy parameter, all subjects in the Primary Randomization Cohort who received the IP, had a baseline observation and at

least one post-baseline observation. Subjects will be summarized and analyzed per their randomization assignment, regardless of the treatment actually received.

Per Protocol Population: Subjects in the Primary Randomization Cohort with no major protocol violations at end of study (EOS). The list of subjects with major protocol violations will be compiled in a blinded fashion prior to database lock at EOS. For the analysis of the primary efficacy endpoint based on the per protocol population, a sensitivity analysis will be done to evaluate the effect of excluding subjects randomized in the wrong cohort or the wrong stratum from the per protocol population; i.e., subjects incorrectly randomized in the Exploratory Randomization Cohort would be excluded from the per-protocol sensitivity analysis, as would subjects randomized in the wrong stratum based on time since index MI (recent vs. chronic).

Exploratory Safety Population: All subjects in the Exploratory Randomization Cohort who received the IP. Subjects will be summarized and analyzed per treatment actually received, regardless of their randomization assignment.

Exploratory ITT Population: All subjects in the Exploratory Randomization Cohort who were randomized. Subjects will be summarized and analyzed per their randomization assignment, regardless of the treatment actually received.

Exploratory mITT Population: For a given parameter, all subjects in the Exploratory Randomization Cohort who received the IP, had a baseline observation and at least one post-baseline observation. Subjects will be summarized and analyzed per their randomization assignment, regardless of the treatment actually received.

## **7. DATA MANAGEMENT, PRESENTATION, AND ANALYSIS CONSIDERATIONS**

### **7.1 Programming Environment**

SAS® Version 9.2 or higher (SAS Institute, Cary, NC) will be used for statistical analyses and the production of tables, figures, and listings (TFLs).

### **7.2 Tables, Figures, and Listings**

TFLs will be produced for the Primary Randomized Cohort; a subset of TFLs will also be produced for the Exploratory Randomized Cohort. Tables of contents for TFLs to be produced are shown in [Appendix C](#). All TFLs will be appended to the final CSR.

#### **7.2.1 Tables and Figures**

- Tables and figures will present data summaries and/or analyses for the appropriate study population; e.g., summaries of safety parameters will be shown for the safety population only.
- Treatment group order in tables and figures will be Recent CAP-1002, Recent Placebo, Chronic CAP-1002, Chronic Placebo, Overall CAP-1002, Overall Placebo.

- Tables and figures will present summaries/analyses by study visit window (see [Section 7.7](#)).
- Table column headers and figure legends will include subgroup sample sizes.

## 7.2.2 Listings

- Listings will present all data collected for all subjects (i.e., the ITT populations) unless the listing applies only to a specific analysis population [e.g., listings of treatment-emergent adverse events (AEs) apply only to safety populations].
- Listings will be ordered by unique subject identifier, study visit window), date, and data collection time.

## 7.3 Data Analysis

- The reference date used for summaries and analyses will depend on the analysis population, as follows:
  - ITT population: randomization date
  - mITT population: IP administration date
  - Safety population: IP administration date
  - Per protocol population: IP administration date
- Categorical variables will be summarized as frequencies and percentages in each category. Percentages will be reported to one decimal place. Unless otherwise noted in Sections 8-10, categorical variables will be analyzed using chi square tests of association or, if any contingency table cell has less than 5 subjects, Fisher's exact test.
- Continuous variables will be summarized by numbers of subjects, means, standard deviations, medians, and ranges. The number of decimal places for minimums and maximums will be the same as the original data. The number of decimal places for means, medians, and interquartile ranges will be the same as the original data plus one. The number of decimal places for measures of variance will be the same as the original data plus two. Unless otherwise noted in Sections 8-10, continuous variables will be analyzed using t-tests. Non-parametric tests and data transformations will be considered for variables with distributions that violate t-test assumptions.
- Data with qualifiers (e.g., “<”) will be listed with but summarized without the qualifier.
- P-values will be presented to two decimal places if  $> 0.01$ , to three places if  $< 0.01$  but  $> 0.001$ , and to four places if  $< 0.001$  but  $> 0.0001$ . P-values  $< 0.0001$  will be presented as “ $< 0.0001$ .”
- Statistical tests will be two-sided and tested at the 0.05 significance level unless otherwise noted in Sections 8-10.
- It is understood that statistical non-significance is not an indicator of equivalence.

## 7.4 Subgroups

- All TFLs will display data by recent vs. chronic MI. For most analyses, including analysis of the primary efficacy endpoint, subjects randomized in the wrong stratum will be analyzed according to time since the index MI, calculated as:

$$\text{time\_since} = \text{infusion date} - \text{index MI date} + 1$$

If `time_since` is  $\leq 90$  days, the subject will be classified as “recent MI”; otherwise, as “chronic MI.” For the analysis of the primary efficacy endpoint based on the per protocol population, a sensitivity analyses will be done to evaluate the effect of excluding subjects randomized in the wrong stratum from the per protocol population and the effect of analyzing subjects according to the strata in which they were randomized.

- Differences in safety and/or efficacy by subgroups defined by the following classifiers may be explored as part of the final analysis:
  - Demographics (age dichotomized by median, sex, race)
  - Baseline DSA mean fluorescence intensities  $< 500$  vs.  $500-1000$  and/or DSA quartiles
  - Donor, stromal cell derived factor 1 (SDF1) level of lot received, master cell bank, and/or other identified measures of potential cell potency
  - CAP-1002 manufactured with a modified process (“P5”)
  - With vs. without biventricular pacing initiated less than three months before the screening MRI or after the start of the study, the rationale being that this may confound functional and physiologic outcomes in patients with ischemic cardiomyopathy, and it can take up to 3 months post-implant for any effect to occur.
  - Baseline infarct size ( $\leq 20\%$  vs.  $> 20\%$  of LV mass)
  - Baseline LVEF (dichotomized by median)
  - Baseline weight (dichotomized by median)

## 7.5 Missing Data

- Listings will present data as reported.
- Missing or partially missing dates that are required for date-dependent definitions [e.g., treatment-emergent AEs (TEAEs), concomitant medications] will be assumed to be the most conservative date possible. For example, an AE with a completely missing start date will be considered treatment-emergent; similarly, an AE that started the same month and year as IP administration but with missing start day will be considered treatment-emergent.
- Handling of missing endpoint data in summaries and analyses for each endpoint is described in Sections 8-10.

## 7.6 Study Period and Time Point Definitions

The following study periods and time points are defined:

Screening Period: the 4-week time period before IP infusion.

Baseline: the last observation of a given parameter before IP infusion of a given subject.

Day 0: the day of planned IP infusion of a given subject.

(Nominal Visit) Analysis Time Point: analysis based on data collected at the *(nominal visit)* time point, where nominal visits are as shown in the table below.

EOS, Subject Level: subject-level EOS is reached after completion of the Month 12 visit or study or discontinuation for any reason.

EOS, Study-Level: study-level EOS is reached when all randomized subjects have either completed the Month 12 visit or have discontinued from the study for any reason.

Long-Term Follow-Up (LTFUP) Period, Subject-Level: the LTFUP period begins after completion of the Month 12 visit and continues until 4 more annual visits have been completed.

## 7.7 Visit Windows

Study visits will include Screening, Day 0, and nominal week or month indicated in the table below. Visit windows will be used in data listings, summaries and analyses and will be based on study day of the observation, defined as:

$$\text{study day} = \text{date of observation} - \text{Day 0 date}$$

Visit windows per protocol and to be used in listings, summaries and analyses are as follows:

Nominal Visit	Nominal Day	Min Day Per Protocol	Max Day Per Protocol	Min Day for Analyses	Max Day for Analyses
Week 2	14	11	17	1	22
Month 1	30	27	33	23	59
Month 3	90	84	96	60	135
Month 6	180	174	186	136	270
Month 12	360	354	366	271	426

where cell entries are study days as defined above. For example, per protocol the Month 1 visit will occur between 27 and 33 days post infusion (Day 0), but for purposes of listings, summaries and analysis all observations dated between 23 and 59 days post infusion will be included in the Month 1 visit window.

Efficacy assessments that occur too late to be included in the Month 12 analysis window will be included in “last observation” analyses (see [Section 9](#)).

For ITT summaries and analyses, study day will be defined as:

$$\text{study day} = \text{date of observation} - \text{randomization date} - X$$

where X is

- for treated subjects, the number of days between randomization and IP administration.
- for untreated subjects, the median of the number of days between randomization and IP administration among treated subjects.

For example, for a subject who received IP 5 days after randomization and who had an assessment 65 days after randomization, the study day for that assessment would be 60 and the assessment would therefore fall into the Month 3 analysis window.

In addition, visit windows based on time of data collection will be defined for cardiac biomarkers as follows:

Nominal Visit	Nominal Hour	Min Hour for Analyses	Max Hour for Analyses
8 Hours Post	8	0.01	12.00
16 Hours Post	16	12.01	20.00
24 Hours Post	24	20.01	28.00

If multiple valid, non-missing observations exist within a given window, the observation to be used will be:

1. the observation closest to the nominal visit day/time in question, or
2. the latest observation if the multiple observations are equidistant from the nominal visit day/time, or
3. the average (arithmetic or geometric, as appropriate) of the observations if the multiple observations have the same actual time point.

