7 STUDY ACTIVITIES

The Schedule of Events for the conduct of this study is shown in [Appendix 1](#).

Subjects may sign consent and start the screening process immediately post-MI (e.g., acute admission at hospital). The following assessments will be permitted within 28 days immediately following the subject's MI: signing ICF, review of medical history, review of concomitant medications, and collection of laboratory samples required for assessment of study eligibility criteria (e.g., eGFR, HbA1c, hepatitis serology, HIV serology, LFTs, hematocrit, WBC, and platelet count). All other screening tests, including the subject's cardiac MRI and CT (chest, abdomen, pelvis), must be conducted greater than 28 days post-MI. Infusion must occur within 28 days of the first screening procedure that is performed greater than 28 days post-MI. Relevant safety laboratory sample collections (e.g., chemistry, hematology, urinalysis) may need to be repeated as they must be obtained within 28 days of the subject's infusion. A subject that rescreens for any reason may be required to repeat all protocol safety procedures (excluding CT of the chest, abdomen and pelvis if previously conducted) if the safety procedures were originally conducted greater than 28 days prior to the subject's infusion. A subject that rescreens for any reason may be required to repeat all protocol efficacy procedures including the cardiac MRI unless: a) the subject's efficacy procedures including baseline cardiac MRI were conducted within 28 days of infusion; **or**, b) the subject's efficacy procedures including baseline cardiac MRI were conducted \geq 60 days post-MI **and** within 60 days of infusion. After completion of the screening procedures and meeting all inclusion and exclusion criteria, study subjects will be randomized to receive CAP-1002 or placebo administered via intracoronary infusion. Study subjects will undergo catheterization and infusion on the day of admission and will be observed in the hospital with continuous cardiac monitoring overnight, 20 to 24 hours afterwards. In the absence of serious adverse events, subjects will be discharged the day after catheterization, with a 24-hour ambulatory ECG monitor.

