7.2 Treatment Period

7.2.1 Intracoronary Infusion Visit (Day 0)

Intracoronary infusion of CAP-1002 or placebo must occur within 28 days of the first screening procedure that is performed greater than 28 days post-MI. At the infusion visit, subjects will be clinically stable as judged by no evidence of infection, stable blood pressure and pulse, as well as over the prior four days by history no change in angina pattern, or in angina or heart failure medications.

As part of the infusion visit, subjects will undergo the following tests and assessments:

Pre-infusion:

- Medical history and cardiac physical examination
- Medication review
- Vital signs
- 12-Lead ECG
- Laboratory tests: hematology, chemistry, urinalysis, serum NT-proBNP, and INR/PTT [as needed for subjects on warfarin (Coumadin®)]; refer to [Table 1](#) for comprehensive list of laboratory tests
- Cardiac enzymes (Serum troponin and CK-MB)

Post-infusion:

- Cardiac assessment
- Vital signs approximately every 8 hours (from infusion time) until discharge
- Cardiac enzymes (serum troponin and CK-MB) approximately every 8 hours x3 with last blood draw immediately prior to discharge (20-24 hours post infusion)
- Urinalysis
- 12-Lead ECG (day of discharge)
- 24 hour ambulatory ECG monitoring (apply to subject immediately prior to discharge)
- Adverse Event assessment

Subjects must have a patent coronary artery with TIMI flow 3 in order for the IP to be infused. Subjects with angiographic evidence of a coronary occlusion determined to be clinically significant, with or without clinical symptoms during the day of IP infusion: 1) will not undergo intracoronary infusion of the IP, 2) will be withdrawn from the study, and 3) will not be followed further for either safety or efficacy. The decision to attempt opening and restoration of TIMI-3 flow will be based on clinical grounds.

Stopping criteria that would trigger halting of the CAP-1002 or placebo infusion are:

1. Sustained hypotension unresponsive to fluids and/or medications.
2. Evidence of acute coronary syndrome.
3. Development of TIMI flow 0/1, after a cycle of infusion.
4. Evidence of cerebrovascular accident.
5. Evidence of cardiac tamponade.
6. Hemopericardium requiring pericardiocentesis.
7. Sustained ventricular tachycardia/ventricular fibrillation that require cardioversion or administration of an antiarrhythmic.
8. Evidence of thrombus in the aorta that was not previously seen on imaging studies.

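### The Week 2 analysis window opens on Day 1, so the 12-lead ECG and vital-sign tables have no discharge time point and the post-discharge ambulatory ECG is labelled Week 2

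*SAP*

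**What the plan says.** SAP 7.7 governs how records reach a table: "Visit windows will be used in data listings, summaries and analyses and will be based on study day of the observation". Study day is the observation date minus the Day 0 date, with no clock time. SAP 7.6 defines Day 0 as the day of planned infusion. In the window table the Week 2 row reads "Week 2 14 11 17 1 22": nominal Day 14, protocol window Days 11 to 17, analysis window Days 1 to 22. When several observations fall in one window, the first rule is to use "the observation closest to the nominal visit day/time in question".

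The only finer windows are in hours: "visit windows based on time of data collection will be defined for cardiac biomarkers as follows". SAP 7.2.1 applies the visit windows to tables and figures. SAP 10.7 (vital signs), 10.8 (12-lead ECG) and 10.9 (ambulatory ECG) make no exception for records taken at discharge.

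Protocol 7.2.1 lists, after infusion, "12-Lead ECG (day of discharge") and "24 hour ambulatory ECG monitoring (apply to subject immediately prior to discharge"), vital signs about every 8 hours until discharge, and a urinalysis. Protocol 7 says that, absent serious adverse events, "subjects will be discharged the day after catheterization, with a 24-hour ambulatory ECG monitor". Protocol 7.3.1 schedules a 12-lead ECG, vital signs, urinalysis and cardiac enzymes at Week 2. Protocol 6.8 schedules ambulatory ECG at screening, after discharge and at Months 1, 6 and 12 for randomized subjects, and not at Week 2.

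**The concern.** The discharge measurements are the first scheduled look at conduction, rhythm and haemodynamics after an intracoronary infusion, in a trial whose SAP introduction names safety as its principal goal. If they are windowed as Week 2, two things go wrong.

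- For the 12-lead ECG and vital signs, a genuine Week 2 record competes with the discharge record and wins. The ECG table then goes from baseline to about Day 14, with no comparison of the arms at about 24 hours. The intervals, rhythm and conduction findings in SAP 10.8 are not summarised when an acute effect would be most visible.
- For the ambulatory ECG nothing competes, so the Day 1 to 2 recording appears under a Week 2 label. A reader would take ectopy counts and arrhythmia indicators from the day after infusion for findings two weeks later.

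A subject who misses Week 2 also contributes Day 1 values to a column in which everyone else contributes values from about Day 14.

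**Working it through.** **Check on the SAP's own figures.** The worked example in 7.7 has infusion 5 days after randomization and an assessment 65 days after randomization: 65 − 5 = 60, which lies in 60–135, so Month 3, as stated. The Month 1 protocol window is 30 ± 3 = 27 to 33, also as stated. The analysis windows are contiguous from Day 1 to Day 426, so every dated record from Day 1 to Day 426 falls into some visit.

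**Step 1: study day of discharge.** The in-hospital stay is 20–24 hours (Protocol 7.2.1). An infusion ending at or after 04:00 gives discharge no earlier than 04:00 + 20 h = 24:00, and one ending before midnight gives discharge before 24:00 + 24 h = 48:00. Both lie on the next calendar day, study day 1. Discharge on Day 0 could arise only for infusions ending between midnight and 04:00.

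**Step 2: window.** Day 1 lies in 1–22, so Week 2.

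**Step 3: which record is kept when Week 2 is attended.**

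| Record | Study day | Distance to Day 14 |
|---|---|---|
| Discharge ECG or vital signs | 1 | 14 − 1 = 13 |
| Week 2 visit within protocol window | 11 to 17 | at most 3 |
| Any other record in the analysis window | 2 to 22 | at most 14 − 2 = 12 |

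Any record on Days 2–22 is closer to nominal than the Day 1 record, so the discharge value is always the one set aside. A later discharge does not change this: for discharge on Day d with 2 ≤ d ≤ 10, the distance is 14 − d ≥ 4, still more than 3.

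**Step 4: Week 2 missed.** If no other value falls on Days 2–22, the discharge 12-lead ECG and last in-hospital vital signs are the subject's Week 2 values.

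**Step 5: ambulatory ECG.** The recording starts on Day 1 and ends on Day 2. Either date maps to Week 2, and no scheduled Week 2 recording competes. The label is off by 14 − 1 = 13 days (start) or 14 − 2 = 12 days (end).

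**Step 6: other records.** A post-infusion urinalysis collected on Day 1 follows the same path as the 12-lead ECG. Vital signs taken on the evening of infusion keep study day 0 and are not drawn into Week 2; those taken after midnight are. Enzymes have the 8-, 16- and 24-hour windows, which SAP 7.7 adds to the day windows. The SAP does not say whether a value used in an hour window can also be used in a day window.

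**The case against.** The strongest reply is that peri-infusion safety does not depend on these tables, and that is largely right. A reader might infer that the window rule hides a peri-infusion safety signal. The documents do not support that:

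- Listings present all data collected (SAP 7.2.2), and the ECG and ambulatory listings carry actual dates and times (SAP 10.8, 10.9).
- Adverse events within 24 hours of infusion have their own listing and summary (SAP 10.3) and are adjudicated (SAP 12).
- Events during and within 24 hours of administration are summarised separately (SAP 8.7; Tables 14.1.8.2 and 14.1.8.3).
- Troponin has hour-based windows.
- Peri-infusion MI, with ECG change among its criteria, is part of the primary safety endpoint.
- Ventricular tachycardia of 30 beats or longer is a secondary safety endpoint analysed as an event rate over follow-up (SAP 2.3.3, 10.2), whatever the visit label.
- The ambulatory values are mislabelled, not lost, and both arms are still summarised.

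These routes report events, however. They do not replace the arm-by-arm summary of ECG intervals, rhythm and vital signs at discharge, nor a correctly timed summary of the first ambulatory recording.

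A second reply is that the discharge records belong to Day 0, because Protocol 7.2.1 and the Schedule of Events place them under the infusion visit and SAP 7.7 names Day 0 as a study visit. That may be what the sponsor intends. But SAP 7.6 defines Day 0 as the day of planned infusion and SAP 7.7 assigns by date, not visit name, so a programmer following the text would send a Day 1 record to Week 2.

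A further tempting inference is that Day 1 troponin and CK-MB become Week 2 values. That needs both a missed Week 2 visit and reuse of a value already placed in an hour window, on which the SAP is silent. It is a gap to close, not an established error.

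**Conclusion.** The point stands as an error in a stated windowing rule. Applied as written, SAP 7.7 leaves the by-visit 12-lead ECG and vital-sign tables without a discharge time point, mixes Day 1 values into Week 2 for subjects who miss that visit, and labels the post-discharge ambulatory ECG as Week 2, when none is scheduled. It reaches essentially every infused subject, about 103 planned in the Primary Randomized Cohort, and the rule is the same for the Exploratory Randomized Cohort. How many subjects would have a Day 1 value standing in for Week 2 depends on missed visits, for which the documents give no rate.

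The effect is confined to descriptive by-visit safety summaries. No primary or secondary endpoint test and no stopping guideline is shown to change.

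The conclusion assumes discharge on the day after infusion, as the protocol plans in the absence of serious adverse events, and takes the date of an ambulatory ECG as either its start or its end. Neither choice of date alters the result.

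**What to change.** In SAP 7.7, add an analysis time point named Post-infusion/Discharge. Assign to it by CRF visit (infusion visit, post-infusion), whatever the discharge date, the discharge 12-lead ECG, the post-infusion vital signs, the post-infusion urinalysis and the post-discharge ambulatory ECG. State that these records, and any enzyme value already assigned to an hour window, are not eligible for the Week 2 window. Add the time point to the tables under SAP 10.5 (urinalysis), 10.7, 10.8 and 10.9.

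Assignment by CRF visit is preferable to a fixed cut-point such as Days 1–4. A subject kept in hospital beyond the cut-point, plausibly because of a problem after infusion, would otherwise fall back into Week 2. The Week 2 limits of Days 1–22 can then stay as they are.

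The cost is SAP wording, the matching programming, and one extra column in the affected tables. No new data are needed, and visits within Days 11–17 are unaffected.
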